2.4.5.3 Deaths

Number (%) of patients who died by study period (on-treatment and post-treatment, within 60 days from first dose of study treatment), and cause of death will be summarized. A listing of patients who died while participating in the study including cause of death, death date, days from first and last dose to death, preferred term, and causal relationship to isatuximab/cemiplimab (when applicable) will be provided.

2.4.5.4 Analyses of laboratory variables

Each laboratory test result will be graded by CTCAE criteria (Version 4.03), when applicable. For hematological parameters and for some biochemistry parameters, sanofi sponsor generic normal ranges will be used for the grading of laboratory abnormalities (see list of parameters in [Table 11](#) and [Table 12](#)). For other biochemistry parameters (eg, for hepatic parameters), grading will be derived using the local laboratory normal ranges.

The number (%) of patients with abnormal laboratory tests at baseline and during the on-treatment period will be presented by all grades and each grade. For patients with multiple occurrences of the same laboratory variable during the on-treatment period, the maximum grade (worst) per patient will be used.

The denominator used for percentage calculation is the number of patients with at least 1 evaluation of the laboratory test during the considered observation period.

When appropriate, the summary table will present the frequency of patients with any grade of abnormal laboratory tests and with Grade 3-4 abnormal laboratory tests.

For eGFR, urea acid, chloride and BUN, potentially clinically significant abnormalities (PCSA) values defined as abnormal values considered medically important by the Sponsor according to predefined criteria/thresholds based on literature review ([Table 8](#)) will be derived. PCSA criteria will determine which patients had at least 1 PCSA during the on-treatment period, taking into account all evaluations performed during the on-treatment period, including nonscheduled or repeated evaluations. The incidence of PCSA any time during the on-treatment period will be summarized by arm and overall, irrespective of the baseline level.

Shift tables showing the number of patients in each grade at baseline by worst grade during the on-treatment period will be provided for selected parameters (eg, anemia, thrombocytopenia, neutropenia and other tests as appropriate).

For creatinine clearance using MDRD formula, the number (%) of patients by category (<15, [15-30[, [30-60[, [60-90[, ≥90 mL/min/1.73m²) and by period (baseline and on-treatment) as well as a shift table will be provided.

Table 8 - Potentially clinically significant abnormalities criteria for laboratory tests

Parameter	PCSA	Comments
Clinical Chemistry		
eGFR (mL/min/1.73m ²) (Estimate of GFR based on an MDRD equation)	
≥15 - <30 (severe decrease in GFR)
 
≥30 - <60 (moderate decrease in GFR)
 
≥60 - <90 (mild decrease in GFR)
 
≥90 (normal GFR)
	
Use is optional
 
FDA draft Guidance 2010
 
Pharmacokinetics in patients with impaired renal function-study design, data analysis, and impact on dosing and labeling

Uric Acid		Harrison- Principles of internal Medicine 17th Ed., 2008
Hyperuricemia	>408 µmol/L	
Hypouricemia	<120 µmol/L	
Blood Urea Nitrogen	≥17 mmol/L	
Chloride	<80 mmol/L >115 mmol/L	

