ASSESSMENT SCHEDULE	Please see Section 1.1 Study Flowchart and Section 1.2 PK/PD.

STATISTICAL CONSIDERATIONS	
Sample size determination:
 
In Phase 1, the actual sample size is expected to vary depending on DLTs observed and number of dose levels explored. The study will follow a standard 3+3 design and 3 to 18 patients might be enrolled.
 
In Phase 2, assuming ORR = 20% in control arm (isa alone arm) and ORR = 50% in combination arms, using Fisher's exact test to compare the ORR in control vs combination arms, given the 1-sided type I error of 5% for each combination arm), 35 patients per arm is required to achieve 79% power for each combination arm). Therefore a maximum number of 105 patients is required in Phase 2 randomization part.
 
A separate anti-CD38 refractory cohort with 15 patients might be enrolled if a treatment benefit is suggested for the combination therapy at the interim analysis including pass the futility check. Assuming ORR =20% or more in the combination therapy, a size of 15 patients is required to test against a null hypothesis of ORR ≤1% (ie, no activity in the Isa alone arm) with a one-sided α of 0.05 and 82% power.
 
Including both Phase 1 and Phase 2 patient, a total of 108 to 138 patients are required.
 
Main Analysis populations:
 
Phase 1 and Phase 2 patients will be analyzed separately. For Phase 1, the all-treated (or safety) population will include all screened patients who received at least 1 dose (even incomplete) of study treatments. For Phase 2, the all treated (or safety) population will include all randomized patients who received at least 1 dose (even incomplete) of study treatments. This population is the primary population for the analyses of exposure and safety parameters.
 
For Phase 2 patients only, the intent to treat (ITT, or randomized) population include all patients with a signed informed consent form who have been allocated a randomization number by the IRT, regardless of whether the patient was treated or not. This population is the primary population for the analyses of efficacy parameters.
 
The PK population will include patients from the treated/safety population with at least one drug concentration after study drug administration (whatever the cycle and even if dosing is incomplete).
 
The anti-drug antibody (ADA, immunogenicity) population will include all patients from the all-treated/safety population with at least 1 available ADA result after the study drug administration.
 
Primary endpoints:
 
A listing of patients with DLTs will be provided for Phase 1 patients.
 
For Phase 1 and Phase 2 patients separately, number (%) of patients experiencing treatment- emergent AEs (TEAE) by primary system organ class and preferred term will be summarized by CTCAE grade (all grades and Grade ≥3) for the all-treated population. Same table will be prepared for drug related TEAEs, infusion associated reactions, TEAEs leading to treatment discontinuation, serious TEAEs and TEAEs with fatal outcome. For patients with multiple occurrences of the same AE within the TEAE period, the worst grade will be used. In addition, adverse events occurring or worsening during the 'extended safety follow-up period' (defined as the time period from 31days after the last dose of study treatments to 90 days after the last dose of study treatments) will also be summarized.
 
Hematology and biochemistry results will be graded according to the CTCAE version 4.03, when applicable. Number (%) of patients with laboratory abnormalities (ie, all grades and Grade ≥3) using the worst grade during the on-treatment period will be provided for the safety population.

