2.1.4 Safety endpoints

The safety analysis will be based on the reported AEs and other safety information, such as clinical laboratory data, vital signs, ECG and ECOG performance status ([Section 1.4](#)).

Observation period

The observation period will be divided into 3 periods: pre-treatment, on-treatment, and post-treatment including the extended safety follow-up period.

- The **pre-treatment period** is defined as the time from when the patient gave informed consent and the start of study treatment administration.
- The **on-treatment period** is defined as the time from the first dose of study treatment up to 30 days after the last dose of study treatment.
- The **post-treatment period** is defined as the time starting the day after the end of the on-treatment period up to the end of the study (as defined in the protocol).
 - The **extended safety follow-up period** is defined as the time period from 31 days after the last dose of study treatments to 90 days after the last dose of study treatments.

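### Chemistry drawn 60 and 90 days after the last dose enters no planned laboratory summary, and the same holds for hematology apart from a possible exception for neutropenia

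*SAP*

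**What the plan says.** **Sampling.** Protocol 1.1 (footnotes j and k) and Protocol 12.4.4.1 schedule blood chemistry, including AST, ALT, bilirubin and creatinine, and hematology at the end-of-treatment visit and again 60 and 90 days after the last dose. Protocol Appendix K (Amendment 01) gives an FDA request as the reason for the two late draws.

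**Periods.** SAP 2.1.4 runs the on-treatment period from the first dose "up to 30 days after the last dose of study treatment". It also defines an extended safety follow-up period as the "time period from 31 days after the last dose of study treatments to 90 days after the last dose of study treatments".

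**Laboratory outputs.** SAP 2.4.5.4 begins: "Each laboratory test result will be graded by CTCAE criteria (Version 4.03), when applicable". Four outputs then state a window:

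- Grade tables: "The number (%) of patients with abnormal laboratory tests at baseline and during the on-treatment period will be presented".
- PCSA incidence: "PCSA criteria will determine which patients had at least 1 PCSA during the on-treatment period".
- Shift tables: baseline grade "by worst grade during the on-treatment period will be provided for selected parameters".
- Creatinine-clearance categories: "by period (baseline and on-treatment) as well as a shift table will be provided".

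The protocol agrees. The synopsis plans laboratory abnormalities "using the worst grade during the on-treatment period will be provided for the safety population", and Protocol 13.4.5.4 uses the TEAE period, which Protocol 13.4.5.2 also ends 30 days after the last dose.

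**Adverse events.** For immune-related AEs, SAP 2.1.4.1 and 2.4.5.2 go past the on-treatment period and include the extended follow-up, on the ground that these events can arise long after exposure.

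**The concern.** Safety of the combination is a co-primary objective. The SAP extends the immune-related AE analysis to day 90 because onset can be late, but does not extend the laboratory analysis over the same days. Hepatitis and nephritis, two of the immune-related toxicities with guidance in Protocol Appendix G, are managed there largely on transaminases, bilirubin and creatinine, which are all measured at days 60 and 90. Those results are collected and graded, yet no by-arm laboratory output shows them. A reader of the study report would see late clinical events without the laboratory data drawn at the same visits.

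**Working it through.** The plan gives no figure to reproduce. The check compares sampling days with analysis windows and then looks for any other output that could carry the late values.

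**1. Overlap of draws and window.**

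- End of on-treatment period (SAP 2.1.4): last dose + 30 days.
- Extended safety follow-up: days 31 to 90, that is 90 − 31 + 1 = 60 days.
- Scheduled draws in that period: 2 (days 60 and 90).
- Overlap with the on-treatment period: 0 of 60 days and 0 of 2 draws.

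Visit tolerance does not change this. The only tolerance stated for these visits is the ±7 days for PK and ADA samples (Protocol 1.2.3 and 1.3.3). If it also applies to safety samples (an assumption), the earliest day-60 draw is 60 − 7 = day 53, still 53 − 30 = 23 days past the end of the window. A late day-90 draw could fall as late as 90 + 7 = day 97.

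**2. Outputs in SAP 2.4.5.4.** All 4 of the 4 outputs that state a window are limited to baseline, the on-treatment period, or both. A further sentence on any-grade and Grade 3-4 frequencies names no period, but it describes how the same summary is presented and adds no late output.

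**3. Other laboratory outputs (SAP 2.4.5.2).**

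| Output | Reaches days 31-90? |
|---|---|
| Thrombocytopenia by grade | No; marked on-treatment |
| Hemorrhage after Grade 4 thrombocytopenia | No; hemorrhages are taken from TEAEs (SAP 2.1.4.1) |
| Neutropenia display | Possibly; no window stated |
| Tumor lysis chemistry | Optional listing of potassium, phosphate, calcium and uric acid, only to support a reported case |

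**4. Ceiling on the unused data.** Phase 2 randomizes up to 105 patients, 35 per arm, so 2 × 35 = 70 are in the combination arms.

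- All arms: 2 draws × 105 = 210 chemistry and 210 hematology panels.
- Combination arms: 2 × 70 = 140 of each.

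Patients still on treatment, dead or lost contribute fewer.

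**5. What the AE route can miss.** Protocol 10.4.1 makes a laboratory abnormality an AE only if it leads to discontinuation or dose modification, is serious, or is an AESI. After the last dose the first two triggers cannot operate. The protocol's AESI list (10.5) refers to Grade ≥3 immune-related events that are treatment-emergent, a period that ends at day 30. A non-serious Grade 3 ALT or creatinine value at day 60, with no diagnosis reported, can therefore go unrecorded as an AE and appear in no planned table.

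**The case against.** The best counter-argument is that late safety is handled on purpose through adverse events. New treatment-related AEs, serious or not, are collected at the day-60 and day-90 visits (Protocol 12.4.4.1). Post-treatment AE and SAE tables are planned, and the immune-related tables run to day 90 both for cemiplimab-related events and regardless of relationship. Protocol 10.3 names an asymptomatic ALT of at least 10 × ULN as an example of a medically important event. The laboratory window is the same in synopsis, protocol and SAP, so nothing promised goes undelivered. This stands: serious events and reported diagnoses are not lost, and the gap is confined to unreported, laboratory-only abnormalities.

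Second, the yield may be small. Protocol 4.2.2.1 reports Grade 3 or higher AST increase in 3 of 353 and ALT increase in 2 of 353 cemiplimab patients. Applied to 70 combination patients, that is 70 × 3/353 ≈ 0.6 and 70 × 2/353 ≈ 0.4 over the whole reporting period. The figures come from another population and count reported AEs rather than laboratory grades, so they do not measure what is missed. They do suggest that a late Grade 3-4 liver table could be nearly empty.

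Third, late values in myeloma mix drug effect with progression and next-line therapy, and thyroid function is not in the Protocol 12.4.4.1 list for the day-60 and day-90 visits. Both points stand. They limit what the table can show and restrict it to description; they do not justify leaving collected safety results without any output.

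**Conclusion.** The point holds. No scheduled day-60 or day-90 chemistry result can enter a planned laboratory summary, nor can any hematology result, except possibly in the neutropenia display. The four windowed outputs cover 0 of 2 scheduled draws and 0 of 60 days.

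This is an analysis choice that can be improved, not an inconsistency. Its likely effect is small and it does not threaten the main conclusion. The ceiling of 210 panels of each type assumes that all 105 patients are treated, stop treatment, and attend both visits. How many patients would have an abnormality that is missed cannot be derived from the documents. The conclusion that neither draw falls inside the window holds at nominal timing and with a ±7-day tolerance.

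**What to change.** In SAP 2.4.5.4, add for the extended safety follow-up period already defined in SAP 2.1.4 a descriptive by-arm summary of worst CTCAE grade for AST, ALT, bilirubin, creatinine/eGFR and hematology. Keep the existing denominator rule: patients with at least one evaluation of the test in the period. At minimum, list Grade 3-4 values.

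- Count the day-90 visit draw when it is taken a few days late, so that visit tolerance does not discard it.
- Flag results obtained after disease progression or after the start of further anti-myeloma therapy.
- State the window of the neutropenia display in SAP 2.4.5.2.

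**Cost.** One extra table or listing and one derived flag. The laboratory data are already collected and to be graded, and SAP 2.1.10 collects the progression and further-therapy dates. No hypothesis test or error rate is affected. The drawback is that some late values will reflect progression or later therapy, so comparison between arms must stay descriptive.

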2.4.5.5 Analyses of vital sign variables

The incidence of PCSAs prior to study treatment administration at any cycle during the on-treatment period will be summarized by arm whatever the baseline level and/or according to the following baseline categories:

- Normal/missing.
- Abnormal according to PCSA criterion or criteria.

The incidence of PCSA during and after study treatment administration at any cycle during the on-treatment period will also be summarized

Table 9 - Potentially clinically significant abnormalities criteria for vital signs

Parameter	PCSA	Comments
HR	
≤50 bpm and decrease from baseline ≥20 bpm
 
≥120 bpm and increase from baseline ≥20 bpm
	To be applied for all positions (including missing) except STANDING.
SBP	
≤95 mmHg and decrease from baseline ≥20mmHg
 
≥160 mmHg and increase from baseline ≥20 mmHg
	To be applied for all positions (including missing) except STANDING.
DBP	
≤45 mmHg and decrease from baseline ≥10 mmHg
 
≥110 mmHg and increase from baseline ≥10 mmHg
	To be applied for all positions (including missing) except STANDING.
Weight	
≥5% increase from baseline
 
≥5% decrease from baseline
	FDA Feb 2007

Temperature and respiratory rate will be summarized at baseline and end of treatment, by arm (and all patients for Phase 1).

A listing of patients with at least one PCSA will be provided.

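### SAP 2.4.5.5: the baseline split of vital-sign PCSAs uses criteria that no baseline value can meet, so its abnormal-at-baseline category is always empty

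*SAP*

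**What the plan says.** SAP 2.4.5.5 states that the incidence of vital-sign PCSAs found before dosing, at any on-treatment cycle, "will be summarized by arm whatever the baseline level and/or according to the following baseline categories". There are two categories: "Normal/missing" and "Abnormal according to PCSA criterion or criteria". A second summary, of PCSAs during and after administration, has no baseline split. A listing of patients with at least one PCSA is also planned.

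Table 9 in the same section is the only definition of a vital-sign PCSA in either document. For heart rate and blood pressure each criterion joins an absolute limit to a change from baseline, for example "≤50 bpm and decrease from baseline ≥20 bpm", "≥120 bpm and increase from baseline ≥20 bpm", "≤95 mmHg and decrease from baseline ≥20mmHg" and "≥160 mmHg and increase from baseline ≥20 mmHg". The weight criteria are changes only, such as "≥5% increase from baseline".

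SAP 2.1.1 defines baseline as a single value per patient, the last one up to the first dose. Protocol 13.4.5.5 has the same two baseline categories but gives no numerical criteria, and defines a PCSA only by reference to predefined criteria or thresholds.

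**The concern.** The second baseline category borrows the on-treatment PCSA definition. A rule that requires a change from baseline cannot be met by the baseline value itself, so the category looks unfillable and the first one would hold every patient.

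At stake is the meaning of the row labels. A reader of the table would take an event in the normal-or-missing row as one that arose in a patient whose vital sign was unremarkable at entry. Some could be patients who were already beyond the limit and worsened further. Such patients can enrol, because the exclusion criteria in Protocol 7.3 set no blood-pressure or heart-rate limit. Vital signs are listed under the primary safety endpoint in the Clinical Trial Summary, and Protocol 4.3.3 gives the isatuximab-alone arm the role of showing what risk cemiplimab adds, so a by-arm table should be labelled correctly.

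**Working it through.** The plan states no figure here to reproduce. The check is to apply each Table 9 criterion to the baseline value.

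**Inputs** (SAP Table 9; baseline definition from SAP 2.1.1):

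| Parameter | Absolute limit | Change required | Change at baseline | Met at baseline? |
|---|---|---|---|---|
| HR, low | ≤50 bpm | fall ≥20 | 0 | no |
| HR, high | ≥120 bpm | rise ≥20 | 0 | no |
| SBP, low | ≤95 mmHg | fall ≥20 | 0 | no |
| SBP, high | ≥160 mmHg | rise ≥20 | 0 | no |
| DBP, low | ≤45 mmHg | fall ≥10 | 0 | no |
| DBP, high | ≥110 mmHg | rise ≥10 | 0 | no |
| Weight, gain | none | rise ≥5% | 0% | no |
| Weight, loss | none | fall ≥5% | 0% | no |

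**Rule.** Let v be the value tested and b the baseline. A high-side PCSA needs v ≥ limit and v − b ≥ d; a low-side PCSA needs v ≤ limit and b − v ≥ d. At baseline v = b, so the change is 0, which is below every d (10 or 20 units, or 5%). The joint condition is false whatever the value of b.

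**Numerical confirmation.** The rules were applied to every whole-number baseline from 20 to 260 for HR, SBP and DBP (241 values each) and from 30 to 200 kg for weight (171 values). The number meeting the full criterion was 0 of 241, 0 of 241, 0 of 241 and 0 of 171. With the absolute limit alone, 172 (HR), 177 (SBP) and 177 (DBP) of the 241 values qualify. These are counts of grid points, not prevalences; they show only that the category can then be filled. Weight has no absolute limit, so it still cannot be classified.

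**Worked example, SBP, baseline 165 mmHg.**
- At baseline: 165 ≥ 160, but the change is 0 < 20. Not abnormal by the criterion, so filed as normal or missing.
- Later value 186: 186 ≥ 160 and 186 − 165 = 21 ≥ 20. This is a PCSA, reported against a normal or missing baseline.
- Later value 170: 170 ≥ 160, but 170 − 165 = 5 < 20. Not a PCSA. The high-side rule is reached only at 165 + 20 = 185 mmHg or more.

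**Other text that might supply a baseline rule.** None does. Protocol 13.4.5.5 gives no separate rule for baseline. SAP 2.4.5.4 is a useful contrast: the laboratory criteria in Table 8 are absolute and could classify a baseline value, yet laboratory PCSAs are summarized without regard to baseline.

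**The case against.** Several points on the other side are sound.

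- **The split is optional.** The two presentations are joined by *and/or*. The one that ignores baseline is fully defined and could be the only one produced. This stands, and it limits the reach of the point.
- **A sensible programmer would use the absolute limit at baseline.** The protocol's wording about values and thresholds leans that way for HR, SBP and DBP. But neither document says so, two programmers could produce different tables, and the reading gives nothing for weight.
- **No decision hangs on the table.** It is descriptive, with no test or stopping rule attached, and the listing keeps individual cases identifiable. This stands.

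A reader might also infer more than the documents support:

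- *Pre-existing abnormalities are counted as new events.* Mostly not. The change condition already keeps a stable abnormal value from being a PCSA, as the value of 170 in the example shows. What is wrong is the baseline label on patients who worsen further from an already extreme value.
- *Patients without a baseline dilute the rate.* Not shown. They cannot meet any Table 9 criterion, but SAP 2.5.3 bases percentages on patients with a non-missing observation, which can be read as excluding them. They should also be few, because Protocol 1.1 requires vital signs at screening and again just before the first infusion.
- *A given number of patients per arm is misfiled.* Assuming 5% to 20% of 35 patients start beyond a limit would give 0.05 × 35 = 1.75 to 0.20 × 35 = 7 per arm. Nothing in the documents supports any part of that range, and it counts everyone beyond a limit, not only those who later have a PCSA.
- *The protocol needs the same correction.* Its text contains no change-from-baseline criterion, so the conflict cannot be shown from the protocol alone.

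**Conclusion.** The point holds as a defect in one optional descriptive table. On the text as written, the abnormal-at-baseline category has a denominator of zero for every parameter in every arm, and a patient who worsens from an already extreme value is reported as a PCSA from a normal or missing baseline. This follows from Table 9 and the single-value baseline definition, and needs no assumption about the data. It does assume that the category is applied literally, since no other rule is given.

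The summary whatever the baseline level, the summary of PCSAs during and after administration, the overall PCSA counts, the listing and the ORR analysis do not change. It would be wrong to conclude that the vital-sign safety analysis as a whole is unreliable. The number of patients affected cannot be derived from the documents.

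**What to change.** In SAP 2.4.5.5, add a sentence stating that, for the baseline split only, HR, SBP and DBP are classed as abnormal by the absolute limit in Table 9 without the change condition: HR ≤50 or ≥120 bpm, SBP ≤95 or ≥160 mmHg, DBP ≤45 or ≥110 mmHg. State that weight is not split by baseline category. Alternatively, remove the split and keep the summary regardless of baseline, which is how SAP 2.4.5.4 treats the laboratory PCSAs.

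Showing patients with a missing baseline in their own row would be clearer but is a matter of layout. Protocol 13.4.5.5 can stay as it is.

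The cost is a few lines of SAP text and, if the split is kept, one derived baseline flag. No new data are needed.
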